2.4.4.3 Multiplicity issues

Not applicable.

2.4.4.4 Additional efficacy analysis(es)

Not applicable.

2.4.5 Analyses of safety data

The summary of safety results will be presented by dose and patient group. Corresponding listings will also be presented.

General common rules

All safety analyses will be performed on the safety population as defined in [Section 2.3.2](#), unless otherwise specified, using the following common rules:

- The baseline value is defined as the last value prior to the first dose of GZ402666 in the TDR12857 study
- The re-baseline values is defined as the last non-missing assessment before patients switch to 20 mg/kg dose for LTS-switch patients.
- The potentially clinically significant abnormality (PCSA) values are defined as abnormal values considered medically important by the Sponsor according to predefined criteria/thresholds based on literature review and defined by the Sponsor for clinical laboratory tests, vital signs, and ECG (PCSA version dated May 2014 [Appendix A])
- PCSA criteria will determine which patients had at least 1 PCSA during the treatment-emergent adverse event period, taking into account all evaluations performed during the treatment-emergent adverse event period, including nonscheduled or repeated evaluations. The number of all such patients will be the numerator for the on-treatment PCSA percentage
- The treatment-emergent PCSA denominator by group for a given parameter will be based on the number of patients assessed for that given parameter in the treatment-emergent adverse event period by dose and patient group on the safety population.
- For quantitative safety parameters based on central laboratory/reading measurements, descriptive statistics will be used to summarize results and change from baseline values by visit and treatment group.
- The analysis of the safety variables will be essentially descriptive and no systematic testing is planned. Relative risks between groups and their 95% confidence intervals may be provided, if relevant.

2.4.5.1 Analyses of adverse events

Generalities

The primary focus of adverse event reporting will be on treatment-emergent adverse events. Pretreatment and posttreatment adverse events will be described separately.

If an adverse event date/time of onset (occurrence, worsening, or becoming serious) is incomplete, an imputation algorithm will be used to classify the adverse event as pretreatment, treatment-emergent, or posttreatment. The algorithm for imputing date/time of onset will be conservative and will classify an adverse event as treatment-emergent unless there is definitive information to determine it is pretreatment or posttreatment. Details on classification of adverse events with missing or partial onset dates are provided in [Section 2.5.3](#).

Adverse event incidence tables will present adverse events grouped by SOC and PT, including the number and percentage of patients experiencing AEs in each SOC/PT category and the associated event counts (see the paragraph below for sorting order). Multiple occurrences of the same event in the same patient will be counted only once in the tables within observation period presented

(pretreatment, treatment-emergent, and posttreatment). The denominator for computation of percentages is the safety population within each patient and dose group.

Sorting within tables ensures the same presentation for the set of all adverse events within the observation period (pretreatment, treatment-emergent, and posttreatment). For that purpose, the table of all treatment-emergent adverse events presented by SOC and PT sorted by the internationally agreed SOC order and decreasing frequency of PTs within SOCs will define the presentation order for all other tables unless otherwise specified. Sorting according to frequency of PTs will be based on the sum of patient counts for the patients in the 20mg/kg dose groups. In the case of the AE by maximal severity tables, the sum of patient counts for the severe AEs from patients in the 20 mg/kg dose groups will be used for the sorting of PTs.

For patients previously assigned to the 5 or 10 mg/kg dose groups in the TDR12857, entered the LTS13769 study, and switched to the 20 mg/kg dose group (LTS-switch group), additional AE summaries, as indicated in respective subsections below, will be generated for comparison of before- and after-rebaseline adverse events in these patients.

Analysis of all treatment-emergent adverse events

The following treatment-emergent adverse event summaries will be generated for the safety population.

- Overview of treatment-emergent adverse events, summarizing number and percentage of patients and number of events with any
 - Treatment-emergent adverse event(s)
 - Severe treatment-emergent adverse event(s)
 - Serious treatment-emergent adverse event(s)
 - Treatment-emergent AESI(s)
 - IARs (protocol- and algorithm-defined)
 - Treatment-emergent adverse event(s) leading to permanent treatment discontinuation
 - Treatment-emergent adverse event leading to death
- All treatment-emergent adverse events by primary SOC, HLT, and PT, showing number (%) of patients with at least 1 treatment-emergent adverse event and number of events sorted by the SOC internationally agreed order. The other levels (HLT, and PT) will be presented in alphabetical order.
- All treatment-emergent adverse events by primary SOC and PT, showing the number (%) of patients with at least 1 treatment-emergent adverse event and number of events, sorted by the internationally agreed SOC order and by decreasing incidence of PTs within each SOC. This sorting order will be applied to all other tables, unless otherwise specified.
 - Additional summaries of before- and after-rebaseline periods will be presented for the LTS-switch group
- All treatment-emergent adverse events by PT, showing the number (%) of patients with at least 1 treatment-emergent adverse event and number of events, sorted by decreasing incidence of PTs.

- All treatment-emergent adverse events regardless of relationship and related by primary SOC and PT, showing the number (%) of patients with at least 1 treatment-emergent adverse event and number of events, sorted by the internationally agreed SOC order. The PT levels will be presented in alphabetical order.
 - Additional summaries of before- and after-rebaseline periods will be presented for the LTS-switch group
- All treatment-emergent adverse events by maximal severity, presented by primary SOC and PT, showing the number (%) of patients with at least 1 treatment-emergent adverse event and number of events by severity (ie, mild, moderate, or severe), sorted by the internationally agreed SOC order and by decreasing incidence of PTs within each SOC.
 - Additional summaries of before- and after-rebaseline periods will be presented for the LTS-switch group
- A by-patient listing of AEs, ADA, and IgE, sorted chronologically, will be presented.

Analysis of all treatment-emergent serious adverse event(s)

- All treatment-emergent serious adverse events by primary SOC and PT, showing the number (%) of patients with at least 1 serious treatment-emergent adverse event and number of events, sorted by the internationally agreed SOC order and by decreasing incidence of PTs within each SOC.
 - Additional summaries of before- and after-rebaseline periods will be presented for the LTS-switch group
- All treatment-emergent serious adverse events regardless of relationship and related to IMP, by primary SOC and PT, showing the number (%) of patients with at least 1 treatment-emergent serious adverse event and number of events, sorted by the internationally agreed SOC order. The PT levels will be presented in alphabetical order.
 - Additional summaries of before- and after-rebaseline periods will be presented for the LTS-switch group
- All treatment-emergent serious adverse events by maximal severity, presented by primary SOC and PT, showing the number (%) of patients with at least 1 treatment-emergent adverse event and number of events by severity (ie, mild, moderate, or severe), sorted by the internationally agreed SOC order and by decreasing incidence of PTs within each SOC.
 - Additional summaries of before- and after-rebaseline periods will be presented for the LTS-switch group

Analysis of all treatment-emergent adverse event(s) leading to treatment discontinuation

- All treatment-emergent adverse events leading to treatment discontinuation, by primary SOC and PT, showing the number (%) of patients and number of events sorted by the internationally agreed SOC order. The PT level will be presented in alphabetical order

Analysis of standardized MedDRA query

A comprehensive programming search of AEs which meet the Standardized MedDRA Query (SMQ) criteria for hypersensitivity and anaphylactic reaction will be used to identify adverse events that potentially are associated with symptoms of anaphylactic and hypersensitivity reaction.

Results of this search will be provided in a by patient listing by group. The most recent version of MedDRA SMQ will be used at the time of analysis. A medical review of these cases will be performed.

A listing of potential immune mediated reactions will be provided. All treatment-emergent adverse events, by standardized MedDRA query (SMQ) and PT, showing the number (%) of patients and number of events with at least 1 PT, sorted by decreasing incidence of PTs within each SMQ.

Analysis of adverse events with AESIs

- Treatment-emergent AESIs by Primary SOC and PT, showing the number (%) of patients and number of events, sorted by the internationally agreed SOC order and by decreasing incidence of PTs within each SOC.
- All treatment-emergent AESIs by maximal severity, presented by primary SOC and PT, showing the number (%) of patients with at least 1 treatment-emergent adverse event and number of events by severity (ie, mild, moderate, or severe), sorted by the internationally agreed SOC order and by decreasing incidence of PTs within each SOC.
- Summary tables of infusion associated reactions (IARs) as defined by the 2 definitions will be presented by Primary SOC and PT for each patient group and dose level.
- All IARs by maximal severity, presented by primary SOC and PT, showing the number (%) of patients with at least 1 treatment-emergent adverse event and number of events by severity (ie, mild, moderate, or severe), sorted by the internationally agreed SOC order and by decreasing incidence of PTs within each SOC.
- A detailed listing of patients who experience IARs including information on severity, seriousness, relationship to IMP, timing from first infusion to the onset of the IAR, IAR definition(s) met, action taken regarding study treatment, other action taken, and patient outcome, will be provided.

Severe cutaneous and immune-mediated reactions

- Treatment-emergent severe cutaneous and immune-mediated reactions by Primary SOC and PT, showing the number (%) of patients and number of events, sorted by the internationally agreed SOC order and by decreasing incidence of PTs within each SOC.

Analysis of pretreatment and posttreatment adverse events

- All pretreatment adverse events will be presented in a patient listing.
- All posttreatment adverse events will be presented in a patient listing.

Kaplan-Meier estimates

- A summary table of Kaplan-Meier estimates of TEAEs by 6-month time intervals will be provided.

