11 STATISTICAL CONSIDERATIONS

The Sponsor will be responsible for data collection and editing, reviewing, and validating all the information in the eCRFs, statistical analysis, and generation of the clinical report.

Prior to locking the database, all data editing will be complete and decisions regarding the evaluability of all patient data for inclusion in the statistical analysis will be made. The rationale for excluding any data from the statistical analyses will be prospectively defined, and classification of all or part of a patient's data as non-evaluable will be completed and documented before the entire database is locked.

All data collected in this study will be documented using summary tables, figures, and patient data listings.

All summary statistics will be computed and displayed overall and by treatment group and scheduled assessment time point. Summary statistics for continuous variables will include n, mean, standard deviation, minimum, median, and maximum. For categorical variables, frequencies and percentages will be presented. Graphical displays will be provided as appropriate.

Any changes to the statistical analysis will be delineated in the statistical analysis plan.

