11.9 EXTENT OF STUDY TREATMENT EXPOSURE AND COMPLIANCE

Number of weeks in the study, the number of study infusions, and the dose received by patients will be summarized using summary statistics. Frequency and percentage of patients remaining on treatment will be summarized quarterly.

Data from all patients who are enrolled in the study will be included in the summary of patient accountability. The frequency and percentage of patients who are enrolled in the study, discontinued from the study, and completed the study, along with reasons for discontinuation, will be summarized.

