1 OVERVIEW AND INVESTIGATIONAL PLAN

1.1 STUDY DESIGN AND RANDOMIZATION

LTS13769 is an open-label, multicenter, and multinational extension study with repeated IV infusions of avalglucosidase alfa. Safety, pharmacokinetic, pharmacodynamic, pharmacogenetic, and exploratory efficacy data will be collected during this long-term study. The population will be patients with Pompe disease who have completed study avalglucosidase alfa TDR12857. Patients who received avalglucosidase alfa intravenous (IV) infusion 20 mg/kg of body weight every other week (qow) in the TDR12857 study will continue to receive the same dose in the extension study, while patients who previously received the 5 or 10 mg/kg qow dose will first continue on the same dose that they received in the TDR12857 study, and then provide consent to switch to the 20 mg/kg qow regimen for the remaining duration of the LTS13769 study (henceforth called the LTS-switch group in this document).

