2.1.4 Safety endpoints

The safety analysis will be based on the reported adverse events (AEs) and other safety information, such as clinical laboratory data, vital signs, ECG, etc.

Observation period

The observation period will be divided into the following epochs:

- The screening epoch is defined as the study period preceding treatment, starting from the signed informed consent date (TDR12857) up to the first administration of IMP. (Note: medications known to have been taken by the patients within 28 days of the TDR12857 screening/baseline visit will be recorded in the CRF as well.)
- The treatment epoch is defined as the time from the start of the first administration of the IMP in the TDR12857 through the completion of the last administration of the IMP.
 - Before- and after-rebaseline periods within the treatment epoch will be used for select analyses
- The residual treatment epoch is defined as the time subsequent to the treatment epoch, from the completion of the last administration of the IMP through the last administration of the IMP + 28 days or the end of the protocol-defined follow-up period, whichever is earlier.

The treatment-emergent adverse event (TEAE) period will include both treatment and residual treatment epochs.

- The **posttreatment** epoch is defined as the period of time starting the day after the end of the treatment-emergent adverse event period up through the end of the study.

The on-study observation period is defined as the time from start of treatment in the TDR12857 until the end of the LTS13769 study (defined as the last follow-up visit as defined in LTS13769 protocol Section 10.1.2.9).

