2.4.3 Extent of investigational medicinal product exposure and compliance

2.4.3.1 Extent of investigational medicinal product exposure

The extent of IMP exposure will be assessed by the duration of IMP exposure, number of infusions, and amount of dose received. The extent of IMP exposure will be summarized in safety population.

Duration of IMP exposure is defined as last dose date – first dose date + 14 day, regardless of unplanned intermittent discontinuations (see [Section 2.5.3](#) for calculation in case of missing or

incomplete data). Duration of IMP exposure will be summarized descriptively as a quantitative variable (number, mean, SD, median, minimum, and maximum). In addition, duration of treatment exposure will also be summarized categorically by numbers and percentages for each of the following categories and cumulatively according to these categories: <6 months, 6 months to <1 year, 1 to <2 years, 2 to <3 years, 3 to <4 years, 4 to <5 years, 5 to <6 years, and \geq 6 years.

The cumulative dose information will be assessed by the total number of infusions received. These data will be summarized descriptively.

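### The before/after-switch adverse event tables for the LTS-switch group carry no patient-years, so they cannot separate a change in event rate from a difference in period length

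*SAP*

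**What the plan says.** SAP 2.4.5.1 states that, for the LTS-switch group, additional AE summaries "will be generated for comparison of before- and after-rebaseline adverse events in these patients". The same line, "Additional summaries of before- and after-rebaseline periods will be presented for the LTS-switch group", is then attached to six tables: TEAEs and serious TEAEs, each as all events, by relationship to IMP, and by maximal severity. All six show number (%) of patients and number of events. On the percentages the section says: "The denominator for computation of percentages is the safety population within each patient and dose group".

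The periods are defined only in SAP 2.1.4: "Before- and after-rebaseline periods within the treatment epoch will be used for select analyses". SAP 1.1 explains how they arise. Patients on 5 or 10 mg/kg "will first continue on the same dose that they received in the TDR12857 study", then consent to 20 mg/kg and stay on it for the rest of LTS13769. No length is set for either part.

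Exposure is handled in SAP 2.4.3.1: "Duration of IMP exposure is defined as last dose date – first dose date + 14 day, regardless of unplanned intermittent discontinuations". Protocol 11.9 adds: "Number of weeks in the study, the number of study infusions, and the dose received by patients will be summarized using summary statistics". Neither is stated to be split at the switch. The one time-based analysis of TEAEs is a Kaplan-Meier table in 6-month intervals (SAP 2.4.5.1), which is not stated to be split or restarted at the switch.

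**The concern.** A percentage of patients with at least one event, and a count of events, both grow with observation time. Put side by side for two periods of unequal length, they differ even if the underlying rate is the same. Here the period before the switch is TDR12857 plus an unspecified time in LTS13769 on the old dose. The period after is whatever remains, less any dropout.

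Safety is the primary endpoint, and these tables are the SAP's own before/after contrast of AEs within the same patients. SAP 2.4.5 calls the safety analysis essentially descriptive, so a reader will judge by comparing the two columns. Without patient-years, a rise cannot be told from longer observation, and similar columns could conceal a real change in rate.

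**Working it through.** The plan gives no figure to reproduce, so the check asks how far the two columns diverge when the true rate does not change.

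**Inputs from the documents**
- LTS Day 1 is at study day 183 (SAP Appendix B, Table 4).
- LTS Month 72 is at study day 2372 (SAP Appendix B, Table 1).
- The move of all patients to 20 mg/kg came with Amendment 03, dated 29 January 2016 (protocol 17.2.3). Amendment 01 is dated 9 December 2013 (protocol 17.2.1). Only the dates are used.

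**Assumptions (not in the documents)**
- The switch occurs s years into LTS.
- First events occur at a constant rate r per patient-year, with no dose effect.
- Follow-up ends at Month 72, with no dropout unless stated.

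**Formulas**
- Before: T_b = 183/365.25 + s = 0.50 + s years
- After: T_a = (2372 − 183)/365.25 − s = 5.99 − s years
- Expected proportion with an event: P = 1 − exp(−rT)
- Ratio of expected event counts: T_a/T_b

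**Results at r = 0.1**

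| s (years) | T_b, T_a (years) | % before vs after | Ratio of % | Ratio of counts |
|---|---|---|---|---|
| 1 | 1.50, 4.99 | 13.9 vs 39.3 | 2.82 | 3.33 |
| 1.5 | 2.00, 4.49 | 18.1 vs 36.2 | 2.00 | 2.25 |
| 2 | 2.50, 3.99 | 22.1 vs 32.9 | 1.49 | 1.60 |
| 2.75 | 3.25, 3.24 | 27.8 vs 27.7 | 1.00 | 1.00 |
| 3.5 | 4.00, 2.49 | 33.0 vs 22.1 | 0.67 | 0.62 |

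**Calendar check.** Suppose a patient entered LTS on the date of Amendment 01 (an assumption) and switched on the date of Amendment 03. That is 781 days, so s = 781/365.25 = 2.14, T_b = 2.64 and T_a = 3.85. The result is 23.2% vs 32.0%, ratio 1.38 (counts 1.46).
- With an assumed 20% a year dropout after the switch, λ = −ln(0.8) = 0.223. The after-period proportion is r/(r+λ) × [1 − exp(−(r+λ) × 3.85)] = 22.0%, ratio 0.95.
- A switch 0.5 years after Amendment 03 (s = 2.64) gives 26.9% vs 28.5%, ratio 1.06.
- A switch 1 year after it (s = 3.14) gives 30.5% vs 24.8%, ratio 0.81.
- The s = 1 row needs LTS entry in about January 2015 or later.

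**Range.** Over s = 1 to 3.5 in steps of 0.25, and r = 0.05, 0.1, 0.2 and 0.4, the ratio of percentages at an unchanged rate runs from 0.65 (s = 3.5, r = 0.05) to 3.06 (s = 1, r = 0.05). With the same dropout after the switch it runs from 0.50 to 1.88.

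**With patient-years.** The expected count is rT, so events divided by patient-years returns r in each period. The rate ratio is 1.00 in every constant-rate scenario above.

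**The case against.** The strongest reply is that the wide range is not tied to this trial. The documents give no entry dates, switch dates, event rates or dropout. Of the four calendar-based cases, three (1.06, 0.95, 0.81) lie within 20% of 1. This stands as a limit on magnitude: the grid shows what is possible, not what happened. It does not rescue the tables, because a reader cannot see whether the periods match unless patient-years are shown.

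Other points, and what remains of them:
- **Saturation.** For very common events the percentages converge. At s = 2.14 the ratio is 1.17 at 0.5 events per patient-year, 1.05 at 1 and 1.00 at 2 (assumed rates). So the distortion of percentages mainly concerns SAEs and less common preferred terms. Counts do not saturate.
- **Counting rule.** SAP 2.4.5.1 counts repeat occurrences of the same event in a patient once per observation period. If that governed the event counts, they would not scale with time. It most naturally governs patient counts, since otherwise the events column would merely repeat the patient column at preferred-term level. The SAP should say so.
- **Horizon.** Treatment can continue past Month 72 in the additional follow-up phase. That would lengthen the after-period and move the break-even point, but the argument is unchanged.
- **Existing outputs.** Protocol 11 promises that "All data collected in this study will be documented using summary tables, figures, and patient data listings", and SAP 2.4.5.1 plans a chronological by-patient AE listing, so person-time could be rebuilt afterwards. The summary tables would still not show it.
- **Limited role.** These summaries are additional and descriptive, and the main objective is long-term safety overall. That bears on priority, but the SAP itself offers them for comparison.

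**Conclusion.** The concern holds. Followed exactly, the plan produces before and after columns that differ at an unchanged event rate whenever the periods differ in length, and no planned output is stated to give person-time split at the switch. Confidence in the omission is high. The size and direction of its effect in this trial are unknown. The illustrative ratios rest on a constant rate, assumed values of s and r, and Appendix B target days. The calendar cases also rest on an assumed LTS entry date. This should be changed: it affects how a contrast on the primary endpoint can be read, and it is cheap to correct.

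**What to change.** In the LTS-switch before/after TEAE and SAE tables:
1. Add patient-years in each period, split at the date of the first 20 mg/kg infusion.
2. Add events per 100 patient-years with 95% CI, by a method that allows for repeat events within a patient.
3. Keep the planned percentages and counts, and state that the count-once rule applies to patient counts only.

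State in the SAP that the rates assume a roughly constant hazard, since they can mislead the other way if events cluster early in treatment. State also that they remove only the period-length artefact. The sequence is always low dose then high dose, so dose stays confounded with time on treatment. Rates will not equalise ascertainment either: biochemistry moves from monthly to quarterly after the first 3 years since enrollment (protocol 10.1.2.2 and 10.1.2.3).

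The cost is SAP wording and a few table columns. Protocol 8.7.1 already requires administration dates to be recorded and dosing information to be entered in the eCRF, so no new data are needed.

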1.3 DETERMINATION OF SAMPLE SIZE

Sample size for the TDR12857 study was based upon empirical considerations. LTS13769 is the extension study of TDR12857; therefore, the number of patients in LTS13769 was determined by the subgroup of TDR12857 patients who consented to continue in the extension study. Thus, no formal sample size calculations have been performed for the TDR12857 or the LTS13769 study.

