2.3 ANALYSIS POPULATIONS

Neither the TDR12857 nor the LTS13769 study was randomized. Patients will be analyzed according to the treatment they actually received instead of the intent to treat (ITT) approach.

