Appendix B Visit windows

The analysis visits are assigned by comparing the distance between the calculated study day of each assessment (defined as time elapsed from the start of study drug in the TDR12857 study till the time of the assessment) with the listed target study days and the corresponding analysis windows of the applicable group of assessments, utilizing the general rules below:

1. If more than one non-missing values are assigned to the same analysis visit, then the assessment performed closest to the target study day will be used in the by-visit analysis.
2. Multiple values assessed on the same date will be averaged prior to being assigned an analysis visit.
3. If two assessments are assessed on different dates but equidistant from the target date, the values assessed on a later date will be used.
4. Use a combination of 2 & 3 in cases where there are multiple records equidistant from the target study day. For example, for a post-baseline visit, if there are 2 records, 7 days before the infusion and 3 records 7 days after the infusion, then take the 3 records after the infusion and average them for analysis value.

All visits in the applicable datasets will be used, including scheduled and unscheduled visits. (For change from TDR12857 baseline analyses, rebaseline visit and assessments performed after rebaseline will be handled in the same manner.) Note that baseline is defined as the latest available observation before the first infusion in the TDR12857.

Table 1 — Analysis windows for 6MWT, PFTs, ECG, hematology, and urinalysis:

VISIT (target study day*)	Analysis Visit	Analysis Visit Window (in study days*)
Baseline	Baseline	
Week 1@ in TDR (1)	Week 1	1 to 42 days
Week 13 in TDR (85)	Week 13	43 to 127 days
Week 25 in TDR (169)	Week 25	128 to 273 days/(1 st day of LTS – 1)**
Month 6 in LTS (365)	Week 52	(1 st day of LTS) to 456 days
Month 12 in LTS (547)	Week 78	457 to 638 days
Month 18 in LTS (730)	Week 104	639 to 821 days
Month 24 in LTS (912)	Week 130	822 to 1003 days
Month 30 in LTS (1095)	Week 156	1004 to 1186 days
Month 36 in LTS (1277)	Week 182	1187 to 1368 days
Month 42 in LTS (1460)	Week 208	1369 to 1551 days
Month 48 in LTS (1642)	Week 234	1552 to 1733 days
Month 54 in LTS (1825)	Week 260	1734 to 1916 days
Month 60 in LTS (2007)	Week 286	1917 to 2098 days
Month 66 in LTS (2190)	Week 312	2099 to 2281 days
Month 72 in LTS (2372)	Week 338	2282 to 2402 days

@ Week 1 visit only applies to ECG, hematology, and urinalysis.

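### The infusion-reaction, AESI and PCSA tables are not split at the switch to 20 mg/kg, and the SAP does not say which dose column holds a switched patient's events

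*SAP*

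**What the plan says.** SAP 1.1 sets out the dose change. Patients on 20 mg/kg in TDR12857 continue on it, "while patients who previously received the 5 or 10 mg/kg qow dose will first continue on the same dose" and then consent to switch to 20 mg/kg; these form the LTS-switch group.

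SAP 2.1.4 provides a device for the switch, but only in part: "Before- and after-rebaseline periods within the treatment epoch will be used for select analyses". For adverse events, SAP 2.4.5.1 says that "additional AE summaries, as indicated in respective subsections below, will be generated for comparison of before- and after-rebaseline adverse events in these patients". The IAR tables, under both the protocol and the algorithm definition, "will be presented by Primary SOC and PT for each patient group and dose level". On percentages: "The denominator for computation of percentages is the safety population within each patient and dose group". On assignment, SAP 2.3 says: "Patients will be analyzed according to the treatment they actually received instead of the intent to treat (ITT) approach".

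For change from the TDR12857 baseline in windowed assessments, Appendix B says that "rebaseline visit and assessments performed after rebaseline will be handled in the same manner". Changes from rebaseline are a separate analysis on rebased visits.

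**The concern.** IARs are named in the protocol's primary endpoint (Section 9.1). Protocol 11.5.3 lists them with TEAEs and SAEs among the events whose incidence is to be broken down by dosing. They are also the events tied most directly to a particular infusion, and so to a particular dose. Yet the SAP splits the TEAE and SAE tables at the switch and leaves the IAR tables whole.

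At stake is whether the report can show how often infusion reactions, AESIs and clinically significant abnormalities occurred in switched patients once they were on 20 mg/kg. Protocol 8.4 makes that the dose for every patient. A row that runs from the first TDR12857 infusion to 28 days after the last one cannot show this for a patient who changed dose part-way.

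**Working it through.** The plan gives no figure to reproduce: it states that "no formal sample size calculations have been performed for the TDR12857 or the LTS13769 study", and the study is descriptive. The check is mainly one of text.

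**1. Which outputs are separated at the switch?**

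| Output | SAP section | Separation specified |
|---|---|---|
| TEAEs by SOC/PT, by relationship, by maximal severity | 2.4.5.1 | before/after rebaseline |
| SAEs by SOC/PT, by relationship, by maximal severity | 2.4.5.1 | before/after rebaseline |
| IARs (both definitions), and by maximal severity | 2.4.5.1 | none |
| AESIs, and by maximal severity | 2.4.5.1 | none |
| PCSAs: laboratory, vital signs, ECG | 2.4.5.3 to 2.4.5.5 | none; counted at any time in the TEAE period |
| By-visit change: 6MWT, PFT | 2.4.4.2 | change from rebaseline |
| By-visit change: laboratory, ECG | 2.4.5.3, 2.4.5.5 | change from rebaseline |
| MRI | 2.4.7 | baseline/rebaseline, plus extra summaries for switchers |
| By-visit change: vital signs | 2.4.5.4 | none; change from baseline only |
| Muscle biopsy, urine Hex4 | 2.4.7 | none; change from baseline only |

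SAP 2.4.5.1 provides the split only where a subsection indicates it, so the absence of a line under IAR or AESI means that no split is planned there.

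**2. Where does a switcher's event go?** The as-treated rule in SAP 2.3 does not cover a patient treated at two doses. Four readings of *dose level* are open:

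- Dose assigned in TDR12857: the 5 and 10 mg/kg columns absorb reactions at 20 mg/kg. The continuous 20 mg/kg column is clean but omits the switchers' experience at that dose.
- One LTS-switch column: that column blends two doses, and the continuous 20 mg/kg column is again clean but incomplete.
- Switchers moved wholly to 20 mg/kg: that column includes reactions at 5 or 10 mg/kg.
- Dose at the time of the event: the table is already separated.

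The last reading fits poorly. All safety results are presented by dose and patient group (SAP 2.4.5), yet the TEAE and SAE tables still need additional before/after summaries. Those would be largely redundant if events were already placed by the dose given. The percentage denominator is also not period-specific. The PT sorting rule in 2.4.5.1 uses patient counts in the 20 mg/kg dose groups without saying whether switchers count there.

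**3. How much could an unsplit row differ from the 20 mg/kg rate?** Assumptions: constant rates, follow-up to study day 2402 (the last day of the Appendix B windows), and a switch on study day 365, 730, 1095 or 1460. The documents give neither switch dates nor event rates.

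Low-dose share of follow-up: w = switch day / 2402. Unsplit rate: R = w × r_low + (1 − w) × r_20. If r_low is half of r_20, then R / r_20 = 1 − w/2. If r_low is twice r_20, then R / r_20 = 1 + w.

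| Switch day | w | R / r_20, low-dose rate half | R / r_20, rates equal | R / r_20, low-dose rate double |
|---|---|---|---|---|
| 365 | 15.2% | 0.92 | 1.00 | 1.15 |
| 730 | 30.4% | 0.85 | 1.00 | 1.30 |
| 1095 | 45.6% | 0.77 | 1.00 | 1.46 |
| 1460 | 60.8% | 0.70 | 1.00 | 1.61 |

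The percentage of patients with any event accumulates even when rates are equal. If 20% have an event in each period, independently, the unsplit row shows 1 − 0.8 × 0.8 = 36%.

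**The case against.** The strongest reply is that post-switch reactions are already tabulated. Both IAR definitions require a relationship to study drug, so every IAR falls within the related-TEAE table, which is split at rebaseline. A detailed IAR listing and a chronological by-patient AE listing are planned as well. This stands in part: no event is lost. But the related-TEAE table also holds related events that are not IARs and cannot separate the two definitions. The content specified for the IAR listing includes neither dose at onset nor a before/after-rebaseline flag.

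Three stronger readings are tempting, and the documents do not support them.

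- *By-visit changes are not separated at the switch.* A reader of Appendix B alone might infer this. Change from rebaseline is planned for laboratory, ECG, 6MWT and PFT, and MRI has rebaseline summaries. SAP 2.5.1 states the purpose as comparison before and after the switch. The gap is confined to vital signs, urine Hex4 and biopsy.
- *The 20 mg/kg results are contaminated whichever way switchers are placed.* Under the first two readings above, the continuous 20 mg/kg column holds only 20 mg/kg experience. It is incomplete, not mixed.
- *Discontinuations due to TEAEs need the same split.* By definition an LTS-switch patient reached the switch, so a permanent discontinuation follows it. In an LTS-switch column a split would add nothing.

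It is also fair to say that the study is descriptive, plans no systematic testing and has few patients, so the extra tables will have small cells.

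**Conclusion.** The point holds in a limited form. The dedicated IAR, AESI and PCSA tables have no before/after-rebaseline summary for LTS-switch patients, although the SAP has that device and uses it for TEAEs and SAEs. The dose column for a patient treated at two doses is undefined. As written, the report need not show IAR incidence after the switch to 20 mg/kg. Vital signs, urine Hex4 and biopsy lack a change from rebaseline.

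The size is unknown. The range of 0.70 to 0.92 rests on assumed switch days and an assumed halving of the rate at the low dose. The direction reverses if reactions were more frequent in the low-dose period, and the bias in the rate vanishes if rates are equal. A reader might take the share of follow-up or infusions at each dose as a measure of error. It shows only how much blending is possible. The case for change rests on the importance of IARs to the primary endpoint and the ease of repair, not on a demonstrated bias.

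**What to change.** - In SAP 2.4.5.1, add before/after-rebaseline summaries for the LTS-switch group to the IAR tables (both definitions) and the AESI tables. In 2.4.5.3 to 2.4.5.5, do the same for the PCSA tables.
- In SAP 2.3 or 2.4.5, define dose group for switchers: each event is assigned to the dose in effect at onset, or for an IAR to the infusion it followed. Use patients exposed in that period as the denominator, and report the number of infusions or patient-years, because every switcher contributes to both periods but for different lengths of time.
- Add change from rebaseline for vital signs (2.4.5.4) and urine Hex4 (2.4.7). For biopsy, at least mark post-switch values in the change-from-baseline displays.

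The cost is SAP wording, programming and more tables with small cells. Dosing information and IAR onset timing are already collected (Protocol 8.7.1 and 10.4.4). Design, sample size and treatment do not change.
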